4-6 weeks following treatment, patients will be reassessed. Three validated questionnaires will be completed, missed days of work tabulated, and falls recorded. Adverse effects will be documented. The assigned treatment will be continued. If inadequately tolerated dose will be reduced to twice daily.

12-14 weeks following treatment, patients will be blindly reassessed. Three validated questionnaires will be completed, missed days of work tabulated, and falls recorded. Adverse effects will be documented. Allocation will be revealed and patients will be offered to start/continue treatment with the active agent.

Figure 1: Study Design

falls during the study period. Finally, participants will be queried regarding their working status and the number of missed days due to vertiginous symptoms in the past three months prior to participation and during the study period. Head or neck imaging and vestibular function study results will be assessed by chart review at the conclusion of the study. The following adverse effects will be recorded at each clinic visit: angina/chest pain, arrhythmia/palpitation; flushing; abdominal discomfort; belching/flatus/bloating; diarrhea; dyspepsia; nausea; vomiting; agitation/nervousness; dizziness; drowsiness; headache; insomnia; tremor; blurred vision.

Medical comorbidities will be reviewed to facilitate subgroup analysis. Determination of treatment effect will be made through implementation of ANOVA testing, through IBM SPSS Statistics software.

Based upon reported data for improvement with pentoxifylline and placebo effect, at an alpha level of 0.05 and beta of 0.2, a power of 80% can be reached with 70 patients per treatment group (140 patients total).³³ We will enroll an extra 20 patients to patient dropout for a total of

160 patients to be enrolled. According to present clinic patterns, we anticipate target enrollment will be reached in approximately 18 months.

Data Handling

All data will be collected both in hard copy and electronic formats. Hard copy data will be stored in a locked office in a locked filing cabinet. Electronic data will be stored on a secure MU network drive that is encrypted and password protected. The research coordinator is responsible for access to both of these locations. Additionally, consents are signed electronically and stored on the secure network drive.

Significance of Research to the Specific Field and Stature of the University:

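### Figure 1 appears to open each patient's allocation at the 12-14 week visit while others are still being enrolled and followed, and nothing keeps opened codes from assessing staff or the analyst

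*Combined protocol and SAP*

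**What the plan says.** Under Project design and Procedures, providers and patients are said to be blinded to arm. In Figure 1, the 12-14 week box begins "12-14 weeks following treatment, patients will be blindly reassessed", lists the questionnaires, missed work, falls and adverse effects, and ends "Allocation will be revealed and patients will be offered to start/continue treatment with the active agent".

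The same section says "we anticipate target enrollment will be reached in approximately 18 months", with 160 patients to be enrolled. Recruitment is in one otolaryngology department.

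Staff-dependent steps during follow-up are the adverse-effect record ("The following adverse effects will be recorded at each clinic visit") and the tolerability judgement in the 4-6 week box ("If inadequately tolerated dose will be reduced to twice daily"). Two further reviews are planned: "Head or neck imaging and vestibular function study results will be assessed by chart review at the conclusion of the study", and "Medical comorbidities will be reviewed to facilitate subgroup analysis". The first has no stated masking; the second has neither timing nor masking. The analysis is given only as ANOVA in SPSS.

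Under Resources and environment, the pharmacy dispenses under a blinding scheme. A senior research coordinator helps with enrolment and data collection and also does the statistical testing. Data Handling adds, of the paper and electronic stores, "The research coordinator is responsible for access to both of these locations".

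**The concern.** A double-blind trial normally keeps its codes from study staff until the data are locked. Here the code seems to open patient by patient, in a small team, while most of the trial is still to run. Two consequences follow.

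First, staff who see completers' arms beside their side-effect histories may guess better at the arm of patients still in follow-up. Such a guess could colour how adverse effects are elicited and recorded, and whether treatment is judged inadequately tolerated.

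Second, the person who will run the tests may hold arm-labelled results before the analysis is settled. This route needs no guessing. Three outcome domains, unnamed subgroups and an unspecified form of ANOVA leave many choices that could be made with the results in view.

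**Working it through.** **1. Does the reveal happen patient by patient?** The box lists the steps of one visit, and the reveal is the last of them. The offer to start or continue the active agent fits a patient who has just finished 12 weeks of treatment. It fits less well if the first patient had to wait for the last of 160. The patient-level reading is therefore the natural one, but no sentence says so, and none defers the reveal to the last visit or to a data lock.

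**2. Does any other statement limit who receives an opened code?**

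| Statement | Covers | Does not cover |
|---|---|---|
| Blinding statement, Project design and Procedures | Providers and patients, in general terms | Coordinator, data collectors and analyst; anyone after the reveal |
| Pharmacy blinding scheme, Resources and environment | Ordering, preparing and dispensing | Release of codes at the reveal |
| Data Handling | Locked and encrypted storage; access under the research coordinator | Separating codes from study data |

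Nothing fills the gap. The testing is to be done when results are available, which does not say that it waits for all patients.

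**3. How much of the trial follows the first reveal?** The plan gives no figure for this. Its inputs are 140 + 20 = 160 patients, about 18 months of enrolment, and visits at 4-6 and 12-14 weeks. I assume uniform accrual and no dropout.

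- 18 months = 18 × 365.25 / 12 / 7 = 78.3 weeks.
- Rate = 160 / 78.3 = 2.044 patients per week.
- With the first reveal at week v and the early visit u weeks after entry, a patient entering at week t has the early visit after the reveal if t > v − u. The number of such visits is 160 − 2.044 × (v − u).

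| v | u | v − u | Early visits before first reveal | Early visits after |
|---|---|---|---|---|
| 12 | 6 | 6 | 12.3 | 147.7 |
| 12 | 4 | 8 | 16.4 | 143.6 |
| 14 | 6 | 8 | 16.4 | 143.6 |
| 14 | 4 | 10 | 20.4 | 139.6 |

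So about 140 to 148 of 160 early visits follow the first reveal. Only the first final visit precedes it, leaving 159 of 160. If instead the clock starts at the first-enrolled patient's reveal at week 14, and others are seen at week 12, about 2 × 2.044 = 4 more final visits come before it.

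If accrual took 12 months (3.066 per week), the early-visit range is 160 − 30.7 = 129 to 160 − 18.4 = 142. At 24 months (1.533 per week) it is 160 − 15.3 = 145 to 160 − 9.2 = 151. Dropout would lower all these counts.

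**4. Which data are open to influence?** The patient's own questionnaires, falls and missed work are gathered before that patient's reveal, and patients supply them. What remains is the adverse-effect record, the tolerability judgement, the comorbidity review that feeds subgroups, and the choice of analysis.

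**The case against.** The strongest reply is that this is a gap in documentation and not a flaw in design. Each patient's outcomes in all three domains are collected blind. The protocol expects only a minimal excess of adverse effects over placebo, so guessing from side effects may be weak. The reveal could be meant for study end. No sentence says that a code is written in the study record, or that the coordinator under Data Handling is the senior coordinator who runs the tests.

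Most of this stands, and it is why the risk is called indirect. It does not remove the point. The plan states a procedure that opens codes and sets no limit on who receives them. The route through the analyst depends neither on side effects nor on the two coordinators being one person.

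A reader might infer more than the documents support:

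- **Compromised outcomes.** The order of steps in Figure 1 does not support this. Falls and missed work are patients' own reports, even where staff write them down.
- **Predictable assignments or biased enrolment.** This needs the method of generating the sequence and any block size to be known to staff. The plan says only that allocation is random, so no such figure can be derived. For the same reason, the number enrolled after the first reveal is not a measure of exposure.
- **Reshaped diagnostic groups.** Diagnosis is a condition of entry, made before randomization. No section says that the end-of-study review of imaging and vestibular results regroups patients; the plan ties only comorbidities to subgroup analysis.

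**Conclusion.** The concern holds in limited form. On the patient-level reading, which is natural but not stated, codes open from the first 12-14 week visit onward. No section keeps them from staff still assessing blinded patients or from the role that will analyse the data. The visit counts rest on uniform accrual and no dropout. They show how much of the trial runs with some codes open, not how far any result would move, and the documents do not allow a bias to be sized. The analysis route deserves most weight, because arm-labelled results could be in hand while the model and subgroups remain unspecified. The change is worth making because it alters a stated procedure at low cost.

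**What to change.** - Amend the reveal sentence in Figure 1 so that the pharmacy holds the code and does not release it to enrolling providers, outcome collectors or the coordinator/analyst until the last patient's 12-14 week data are locked.
- If patients are to be told individually, have the pharmacy tell them, and keep the allocation out of the study record until lock.
- Amend the chart-review and comorbidity sentences so that both reviews are complete, and subgroup labels fixed, before codes are released to study staff.
- The investigators should reconcile the reveal sentence with the statement that providers and patients are blinded. They should also decide how the offer of the active agent, and any release needed for a patient's care, will be handled.

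The cost is three reworded sentences, some rescheduling of reviews already planned, and a small added pharmacy task. On the same accrual assumption, staff would learn allocations later by up to about 78 weeks for the first patient and 78.3 / 2 = 39 weeks on average, plus lock time. Clinic staff may not know a patient's earlier arm when the active agent is offered; whether that is acceptable is for the investigators. If patients are told individually, some may disclose their arm, so protection would be partial.

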Betahistine has demonstrated efficacy for treatment of Ménière's disease and other vertiginous syndromes in randomized, placebo-controlled trials. ^{25,26} Piracetam can alleviate vertigo after head injury, vertigo in vertebrobasilar insufficiency and in peripheral vestibular disorders. ²⁷

Ginkgo biloba extract EGb 761 is effective for treatment of vestibular and non-vestibular vertigo in randomized placebo controlled trials. ²⁸ When betahistine and ginkgo biloba extract EGb 761 were directly compared in patients with peripheral vertigo not otherwise specified or vertiginous syndrome not otherwise specified similar efficacy was observed in both groups with fewer adverse effects from ginkgo biloba 761. ²⁸

Studies have also investigated the use of pentoxifylline for vascular causes of imbalance as it is known to increase erythrocyte flexibility and decrease blood viscosity, thereby improving microvascular blood flow.²⁹ Cesarone et al. performed a placebo—controlled, randomized trial, of pentoxifylline for vascular inner ear disease using a dose of 1800 mg per day and found a statistically significant increase in cochlear blood flow of 287.5% in the pentoxifylline group versus 168% in the placebo group.³⁰ Importantly, the increase in flow brought the cochlear flow in the treatment group up into the reported normal range while the placebo treated individuals flow remained reduced.³⁰ In a separate report utilizing the same patient population, Incandela et al. found a 44.1% larger reduction in symptoms including vertigo, dizziness, tinnitus, and hearing loss in the pentoxifylline group than the placebo group.³¹ In another study, Hartmann et al. studied regional cerebral blood flow, as measured by xenon 133 inhalation, among patients with reduced cerebral blood flow due to vascular disease in an open, randomized controlled, format.³² The authors found that use of pentoxifylline and the ergot alkaloid co-dergocrine

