Potential participants will be excluded if any of the following diagnoses are made: benign paroxysmal positional vertigo, Ménière's disease, vestibular migraine with headache, intracranial mass, perilymphatic fistula, or multiple sclerosis. In addition, individuals will be ineligible if there is history of cholesteatoma, prior ear surgery other than myringotomy and tube placement, prior radiation therapy to the head and neck, or previous use of vestibulotoxic medications where the enrolling provider determines the drug exposure to be the cause of imbalance. Use of blood thinning medications or intolerance/allergy to pentoyifylline or methylxanthines, as well as recent cerebral or retinal hemorrhage (past 3 months), will result in exclusion. Females must not be pregnant or lactating and individuals must use adequate contraception during the study period. Females of child bearing potential will be administered a pregnancy test prior to starting the study medication.. Use of any other medications to control vertiginous symptoms and participation in vestibular rehabilitation during the study period will be prohibited.

Patients electing to participate will be randomized to receive either 400 mg of pentoxifylline three times daily for 12 weeks or placebo three times daily for 12 weeks. Allocation will be made randomly and providers and patients blinded to treatment arm. Study medications will be provided to participants at no cost, and plant cellulose will be used as placebo. Outcomes will be measured in three domains: quality of life (handicap), symptom severity, and functionality. Data will be obtained prior to initiation of therapy and at designated time intervals into treatment: 4-6 weeks and 12-14 weeks (Figure 1).

The Dizziness Handicap
Inventory will be used to assess
quality of life, the European
Evaluation of Vertigo for symptom
severity, and the Vestibular
Activities and Participation
Measure to assess functionality.
Patients will be asked to report the
number of falls in the preceding 3
months as well as document any

All patients presenting to University of Missouri Department of Otolaryngology Head and Neck Surgery with imbalance, dizziness, or vertigo will be screened according to inclusion/exclusion criteria.

All individuals meeting inclusion criteria without exclusion will be offered participation.

Patients will be randomly allocated into the active treatment or placebo group in double blind fashion.

70 "Placebo"

70 "Pentoxifylline"

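### The adverse-effect list has no prompt for bleeding, allergy or any unlisted event, and no new-or-worse rule for symptoms that patients may already have at entry

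*Combined protocol and SAP*

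**What the plan says.** The content of adverse-effect recording is specified once, in Project design and Procedures, in the text that follows Figure 1: "The following adverse effects will be recorded at each clinic visit". The list reads: "angina/chest pain, arrhythmia/palpitation; flushing; abdominal discomfort; belching/flatus/bloating; diarrhea; dyspepsia; nausea; vomiting; agitation/nervousness; dizziness; drowsiness; headache; insomnia; tremor; blurred vision". No wording marks it as a set of examples.

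Figure 1 adds one general sentence at each of the two follow-up visits (4-6 and 12-14 weeks): "Adverse effects will be documented". It gives no definition, question or seriousness category and does not mention the list.

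The eligibility paragraph of the same section excludes patients for "Use of blood thinning medications or intolerance/allergy to pentoyifylline or methylxanthines", and adds that "recent cerebral or retinal hemorrhage (past 3 months), will result in exclusion". It gives no reason for either exclusion.

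To enter, a patient must have vertigo, dizziness or imbalance as the chief concern and score at least 16 on the Dizziness Handicap Inventory.

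**The concern.** The events that the exclusions most naturally point to, bleeding and hypersensitivity, are the ones for which the list has no entry. Nor does it have a line for anything unforeseen. An event that nobody asks about is reported only if the patient volunteers it and the staff choose to write it down. A count of zero bleeds would then be uninformative, in either arm.

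This matters because the Preliminary work/results section describes the drug's safety favorably and treats that as a reason to use it if it works. Figure 1 also offers active drug to all participants after unblinding. Readers will look to this trial for safety evidence, and adverse-event data not gathered at the visits cannot be reliably recovered later.

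A second weakness lies in the same list. Dizziness is an adverse-effect item in a trial of patients with dizziness, vertigo or imbalance. Without a rule that only new or worsened symptoms count, an entry may reflect the disease, or lack of benefit, rather than the drug.

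**Working it through.** **1. Text check.** The list has 16 entries: two cardiac, flushing, six gastrointestinal, six nervous-system or behavioral, and blurred vision. Entries for bleeding, bruising or hemorrhage: 0. Entries for rash or allergy: 0. Open or 'other' entries: 0.

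**2. Other routes by which a bleed might be captured.**
- Figure 1's general sentence permits a note but prompts nothing.
- Headache or blurred vision might accompany a cerebral or retinal bleed, but recording the symptom does not identify the bleed.
- The plan states that "Head or neck imaging and vestibular function study results will be assessed by chart review at the conclusion of the study". It is not described as safety collection, and MRI is done at the enrolling provider's discretion.
- The document contains no definition or reporting route for serious adverse events, no laboratory safety tests and no safety monitoring.

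**3. Would there be anything to find?** The plan gives no figure to reproduce and no bleeding rate, so the risks below are assumptions. Patients per arm come from the sample-size paragraph: 160 enrolled gives 160/2 = 80 under equal allocation (Figure 1 shows 70 and 70), or 70 if all 20 spare patients drop out, evenly between arms.

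Chance of at least one event in the active arm = 1 - (1 - p)^n:

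| Assumed risk p | n = 80 | n = 70 |
|---|---|---|
| 0.5% | 1 - 0.995^80 = 33% | 1 - 0.995^70 = 30% |
| 1% | 1 - 0.99^80 = 55% | 1 - 0.99^70 = 51% |
| 2% | 1 - 0.98^80 = 80% | 1 - 0.98^70 = 76% |
| 3% | 1 - 0.97^80 = 91% | 1 - 0.97^70 = 88% |

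**4. What a properly asked zero would be worth.** With no events among n patients who were all asked, the one-sided 95% upper bound on the rate is 1 - 0.05^(1/n):
- n = 80: 1 - 0.05^(1/80) = 3.7%
- n = 70: 1 - 0.05^(1/70) = 4.2%

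Without systematic asking, neither bound applies, because the chance that an event is recorded is unknown.

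**5. The disease-overlap items.** Suppose a fraction b of patients would have dizziness recorded because of their disease, and the drug causes dizziness in a fraction d, independently of the disease. The recorded rate on drug is b + (1 - b)d, so the difference between arms shrinks from d to (1 - b)d. As an illustration only, with b = 90% and d = 10% (both assumed), the rate moves from 90% to 0.90 + 0.10 x 0.10 = 91%, a one-point difference. A smaller b gives less dilution. The documents give no value for b or d. They tie dizziness directly to the condition; for nausea and headache the overlap is plausible, but they do not quantify it.

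**The case against.** The strongest reply is that the list is not closed. The plan does not say that only these effects are recorded, and Figure 1's sentence is unrestricted, stands by itself and does not refer to the list. The two can be read as a general duty plus a set of prompted items. That stands. A reader might infer that a bleed would go unrecorded or has no field on the form. The documents do not support that: a bleed could be noted, and the case report form is not among the documents and might hold an open line. What the text does show is that no systematic prompt is planned.

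The reason for the exclusions is also an inference. A reader might take the protocol to declare bleeding a hazard of the drug, but it never does. Its remark that "it is known to increase erythrocyte flexibility and decrease blood viscosity" explains the hoped-for benefit and does not mention bleeding. The inference is reasonable, and should be stated as one.

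It would likewise go too far to say that no baseline is taken. Recording at each clinic visit may include the visit before treatment, and the dizziness questionnaires are completed before therapy. What is missing is an explicit statement that the list is completed before the first dose, and a rule for using that baseline. Randomization balances background symptoms in expectation, so the cost is lost sensitivity rather than bias.

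Finally, the plan specifies no between-arm safety analysis, and its objectives concern efficacy. That limits the consequence: no planned result becomes wrong. It does not remove the gap, since adverse effects are to be collected and the data should be usable.

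**Conclusion.** The concern holds as a gap in systematic collection. The only specification of adverse-effect content is 16 symptoms with no bleeding, allergy or open item, so an absence of recorded bleeds in this trial could not be read as an absence of bleeding. This rests on the text alone and needs no assumed rate.

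Its practical size depends on a bleeding risk that the documents do not give. Over the assumed range of 0.5% to 3%, the chance of at least one event among 80 active patients runs from 33% to 91%. An event is plausible, but missed events are by no means near-certain. What is given up is the ability to exclude rates above roughly 3.7% to 4.2% if none were found.

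The disease-overlap point is secondary: dizziness, and plausibly nausea and headache, would partly count the condition and be less sensitive to a drug effect, by an amount that cannot be determined from the documents. The efficacy analysis, sample size and alpha are unaffected. This is a cheap improvement worth making, not a flaw that invalidates the trial.

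**What to change.** In Project design and Procedures, amend the adverse-effect list as follows:
- Add any bleeding or bruising; allergic reaction or rash; and an open line for any other new symptom or event, with a yes/no field for seriousness.
- State that the list is completed before the first dose as well as at both follow-up visits.
- State that events new or worse than baseline will be tabulated by arm.

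If the case report form already has an open line or a pre-dose completion, the protocol need only say so.

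The cost is a few extra lines on the form, slightly longer visits and, if not already intended, one additional completion before treatment. No procedure, eligibility rule, sample size or efficacy analysis changes.

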mesylate resulted in increased flow but a much more pronounced effect was seen with pentoxifylline.³² Interestingly, the pentoxifylline treated group showed preferential improvement in flow among the more ischemic brain tissue, and patients reported improvements in sleep disturbances, vertigo, and tinnitus.³² The selective improvement in flow among areas that are relatively ischemic is felt to be associated with the hemorrheologic mechanism of pentoxifylline and is proposed to be unique to drugs that work in this way without such beneficial effects in other medications such as vasodilators.³² While these reports suggest that pentoxifylline use is beneficial, small numbers of patients were included and non-validated instruments were used to measure symptomatic improvement. Therefore, further investigation into the efficacy of pentoxifylline for treatment of imbalance due to vascular etiologies is necessary, including identification of particular subsets of patients most likely to benefit from treatment. Many trials in varied populations demonstrate that pentoxifylline has an excellent safety profile with minimal increase in adverse effects over placebo making it an ideal agent to study and use if efficacy is demonstrated.^{29,30,32}

Project design and Procedures:

Adults, 18 years of age and over, presenting to the University of Missouri Department of Otolaryngology Head and Neck Surgery with chief concern of vertigo, dizziness, or imbalance will be considered for study. All individuals will undergo comprehensive clinical evaluation including otoscopic examination and testing of cerebellar function, gait observation, and dix hallpike maneuver. Additionally, all individuals will receive an audiogram and complete preintervention balance questionnaires, per standard of care. MRI of the brain/internal auditory canal as well as formal vestibular function testing will be conducted at the discretion of the enrolling provider. Individuals diagnosed with multisensory losses, presbystasis, bilateral

vestibulopathy, central vascular insufficiency, small vessel circulatory disease, generalized imbalance, and idiopathic peripheral vertigo scoring at least 16 on the Dizziness Handicap Inventory will be offered participation in the study. Patients must have sufficient English skills to complete the required surveys.

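### None of the 16 adverse effects asked about is bleeding or bruising, and no route is given for unlisted or serious events, so an absence of reported bleeding would be uninformative

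*Combined protocol and SAP*

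**What the plan says.** All of the relevant text is in the protocol's section *Project design and Procedures*, except where noted.

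- **What is recorded.** The text after Figure 1 says: "The following adverse effects will be recorded at each clinic visit: angina/chest pain, arrhythmia/palpitation; flushing; abdominal discomfort". It continues: "belching/flatus/bloating; diarrhea; dyspepsia; nausea; vomiting; agitation/nervousness; dizziness; drowsiness; headache; insomnia; tremor; blurred vision". The list ends there.
- **General statement.** Both follow-up boxes of Figure 1 (4-6 weeks and 12-14 weeks) say "Adverse effects will be documented", with no method and no reference to the list.
- **Exclusions.** Two criteria bear on bleeding: "Use of blood thinning medications or intolerance/allergy to pentoyifylline or methylxanthines" and "recent cerebral or retinal hemorrhage (past 3 months), will result in exclusion". No reason is given for either.
- **Other data that might touch on bleeding.** Falls are counted at each follow-up. Imaging is handled retrospectively: "Head or neck imaging and vestibular function study results will be assessed by chart review at the conclusion of the study". Brain MRI is left to the enrolling provider's discretion.
- **Background on safety.** *Preliminary work/results* describes the drug as lowering blood viscosity and says, of earlier trials, that "pentoxifylline has an excellent safety profile with minimal increase in adverse effects over placebo".

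The protocol defines no serious adverse event, no procedure for reporting one, and no bleeding outcome.

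**The concern.** The plan appears to screen for a risk at entry and then not ask about it on treatment. The exclusions, read with the stated effect on blood viscosity, suggest that bleeding was in the authors' minds. The list of effects asked about covers cardiac, gastrointestinal and nervous-system symptoms, flushing and blurred vision, but not bleeding.

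The stake is how a silent record would be read. If bleeding is not asked about, a table of the listed effects shows none whether or not any occurred. A reader could take that as agreement with the favourable safety statement in the background. *Background and Rationale* also describes falls as common in older adults with disequilibrium, with major injury after some falls in community-dwelling older adults. Those figures do not carry over directly to adults aged 18 and over followed for 12 weeks, and major injury is not the same as bleeding. They make bleeding after a fall plausible in part of the sample and do no more than that.

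**Working it through.** **Step 1. Count the list.** Splitting at the semicolons and the single comma gives: angina/chest pain; arrhythmia/palpitation; flushing; abdominal discomfort; belching/flatus/bloating; diarrhea; dyspepsia; nausea; vomiting; agitation/nervousness; dizziness; drowsiness; headache; insomnia; tremor; blurred vision. That is 16 items. Items naming bleeding, hemorrhage or bruising: 0. Open or 'other' items: 0. Items marking seriousness: 0.

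**Step 2. Look for another route to bleeding data.**

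| Source in the protocol | Does it ascertain bleeding? |
|---|---|
| General sentence in Figure 1 | It could admit a volunteered bleed; no method is stated, so completeness is unknown |
| Headache, blurred vision, abdominal discomfort | Non-specific; would be tabulated under those names |
| Fall counts | Count falls; no injury or bleeding outcome is mentioned |
| Imaging by chart review | MRI is discretionary, no safety purpose is stated, and head or neck imaging cannot show gastrointestinal bleeding or bruising |

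None of these asks every patient in both arms about bleeding.

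**Step 3. What solicited capture would give.** The protocol plans 70 patients per arm (160 enrolled in total, so up to 80 per arm if split equally). It gives no bleeding rate. The 12-week risks *p* of 1%, 2% and 5% below are assumptions, for any bleed in one arm whether drug-related or not.

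The chance of at least one recorded event is 1 − (1 − c·p)^n, where c is the fraction of bleeds captured:

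| | p = 1% | p = 2% | p = 5% |
|---|---|---|---|
| n = 70, c = 1 | 51% | 76% | 97% |
| n = 70, c = 0.5 | 30% | 51% | 83% |
| n = 80, c = 1 | 55% | 80% | 98% |

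For example, with n = 70, c = 1 and p = 1%: 1 − 0.99^70 = 0.505.

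**Step 4. What a zero would mean with full capture.** The exact upper limit for 0/n is 1 − α^(1/n).

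- n = 70, one-sided 95%: 1 − 0.05^(1/70) = 0.042, or 4.2%.
- n = 70, two-sided 95%: 1 − 0.025^(1/70) = 0.051, or 5.1%.
- n = 80: 3.7% and 4.5% respectively.

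These limits apply to the captured risk. If a fraction c is captured, the limit on the true risk is the figure above divided by c: with c = 0.5 and n = 70, 4.2%/0.5 = 8.4% one-sided. When c is unknown and may be near zero, there is no usable limit. That is the position under the present text.

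**Step 5. Comparison between arms.** For k bleeds against none with 70 per arm, the two-sided Fisher p-value is 2·C(70,k)/C(140,k). This is 0.058 for k = 5 and 0.028 for k = 6, so a split of 6 to 0 is the smallest that reaches 0.05. Power of that test at 70 per arm is about 8% for 5% against 1%, about 4% for 5% against 2%, and under 1% for 2% against 1%. Better recording will not turn this trial into a test of bleeding risk.

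**The case against.** A reader might infer that the list is closed, that the trial therefore cannot detect bleeding, and that a clean bleeding record is guaranteed in advance. The documents do not support that. The protocol says that the named effects will be recorded; it does not say that only these will be. Figure 1 states a general duty to document adverse effects, and a checklist of solicited symptoms on top of such a duty is an equally natural reading. The visit form is not in the documents, so whether it has a free-text field is unknown. A reader might also infer that the exclusions declare bleeding to be a known hazard of the drug. The text gives no reason for them.

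Further points on the other side are fair. Safety is not among the stated objectives, and the outcomes are quality of life, symptom severity and functionality. No bleeding summary is planned, so a misleading one is a possibility and not a planned output. The favourable safety statement is about earlier trials. The risks assumed in the working cover anything from bruising to intracranial bleeding, and no single rate fits that range. Even with full capture the trial could compare bleeding between arms only very weakly.

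These points remove the strong reading and limit the importance of the issue. They do not remove the gap: the protocol asks about 16 named effects, none of them bleeding, and is silent on how anything else is recorded. A general sentence without a method leaves capture dependent on what patients volunteer and staff choose to write down.

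**Conclusion.** The point holds as a gap in ascertainment. Bleeding is not solicited and no procedure is given for unlisted or serious events, so an absence of reported bleeding could reflect either no events or no question. It would be uninformative.

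The size is modest. Complete capture would allow a zero in 70 to be stated as excluding risks above about 4.2% (one-sided 95%) or 5.1% (two-sided 95% limit). The present text supports no bound. The gain is an interpretable safety statement, not a powered comparison.

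The conclusion rests on the protocol's text alone, without sight of the visit form. If that form already has a bleeding question and an open field, the remaining task is to say so in the protocol. No efficacy outcome or analysis is affected. This is a cheap improvement.

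**What to change.** In *Project design and Procedures*, where the adverse effects are listed:

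1. Add a solicited item: *any bleeding or bruising (including intracranial, retinal and gastrointestinal)*.
2. Add an open item: *other adverse event*, with a serious yes/no flag.
3. State that both are asked in the same way in both arms at each visit and tabulated by arm.
4. State that any zero count is reported with its upper confidence limit, using the number of patients actually assessed, and that the trial has little power to compare bleeding between arms.

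The cost is a few lines on the visit form, one or two sentences in the protocol, and some free-text events to code. No extra visit, test or patient is needed.
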